6.5.10 Imaging Core Laboratory

The objective of the Imaging Core Lab is to provide an unbiased assessment of the rate of revascularization defined by mTICI scores based on angiographic imaging from the study sites. The Core Lab will review all angiograms obtained. Data provided by the Core Lab will serve as the 'gold standard' and will be used for data analysis and determination of device efficacy. Each angiogram will be read independently by two experienced Core Lab neurointerventionalists. Any discrepancies in mTICI scoring will be resolved by a third, independent reader.

The Core Lab will also have the responsibility to evaluate CT/MRI examinations to detect and assess hemorrhages. Hemorrhages will be radiologically classified as described in section 7.1.

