7.1 Cerebral CT or MR Imaging

This study will collect imaging data in line with routine practice as follows:

- Pre-procedure CT/ MR imaging
- Pre-treatment angiogram, post-device placement angiogram (if this was performed) & post-procedure angiogram
- 24(-8/+12) hour CT/ MR imaging

All imaging should be in line with standard of care. No extra imaging should be performed for the purpose of the study. No patient should be exposed to extra radiation as a result of participation.

Any other imaging performed (for example as a result of clinical deterioration) will also be provided.

In the event of abrupt neurologic deterioration or when deemed necessary by the investigator, an emergency CT or an MR imaging evaluation should be performed. An immediate evaluation of the presence/absence of hemorrhage, edema, and/or infarction as contributors to the clinical deterioration will be made. Any imaging taken prior to the routine 24hr imaging (which may be taken in a time window of 16-36 hours without becoming a protocol deviation) for this reason will be included in the analysis.

Cerebral hemorrhage is categorized as hemorrhagic infarct or parenchymal hematoma by the following definitions:

- *Hemorrhagic infarct* is any area of petechial or small, confluent hemorrhages within larger regions of hypodense, ischemic injury without mass effect.
- A *parenchymal hematoma* is a more homogenous area of hemorrhage, with or without intraventricular extension, usually with mass effect.

Hemorrhages will be classified clinically and radiologically according to the following categories [4]:

Clinical categories:

- C1: Clinical deterioration where hemorrhage is the primary cause < 4 NIHSS points
- C2: Clinical deterioration where hemorrhage is the primary cause \geq 4 NIHSS points

Radiological categories:

- HI 1: small petechiae within the ischemic field without mass effect
- HI 2: confluent petechiae within the ischemic field without mass effect
- PH 1: Hematoma within ischemic field with mild space occupying effect but involving $\leq 30\%$ of the infarcted area
- PH 2: Hematoma within ischemic field with space occupying effect involving $>30\%$ of the infarcted area
- RIH: Any intraparenchymal hemorrhage remote from the ischemic field
- IVH: Intraventricular hemorrhage
- SAH: Subarachnoid hemorrhage
- SDH: Sub Dural Hematoma
- EDH: Extra Dural Hematoma

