At study completion summaries of each clinical outcome variable will include corresponding 95% confidence intervals in order to provide an estimate of the corresponding population means, medians and proportions.

The following primary efficacy endpoint will be examined using the model discussed:

- Revascularization measured using modified Thrombolysis in Cerebrovascular Infarction (mTICI inclusive of the 2c rating). Successful achievement of the endpoint is defined as achieving a mTICI score of 2b or greater in the target vessel, following 3 or less passes of the EmboTrap device.

The primary safety endpoint will be evaluated descriptively:

- The primary safety endpoint will be the rate of sICH together with SADEs (excluding those already counted in sICH).

The secondary endpoints will be examined descriptively to further advance the safety and efficacy profile of the device. Full definitions are provided in section 3.2 of this protocol:

Demographics, baseline characteristics, procedural information, and clinical outcomes (efficacy and safety) will also be summarized.

The study will also perform subgroup analyses of descriptive statistics for the cohort based on

- Specific vascular location of the occlusion (i.e. proximal M1/ distal M1 /M2, etc.)
- Technique of treatment as described below
 - Use of a balloon guide vs. no balloon guide
 - Use of an intermediate catheter vs. no intermediate catheter

A summary of the proportions of subjects receiving each category score on the mTICI scale will be reported.

Note that adverse events will be adjudicated as to the relationship to the EmboTrap device, procedure or the disease state as well to the severity of the event. Subgroup analyses of the points described in the synopsis will be completed.

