14.1 Adverse Events

Any adverse events which occur during or after the procedure (up to the 90 day follow-up) will be recorded in the database and documented in the Clinical Study Report (CSR). Adverse events will be adjudicated as to the relationship to the EmboTrap device, procedure or the disease state as well to the severity of the event. Subgroup analyses of the points described in the synopsis will be completed.

An AE that occurs after the ICF has been signed and before the treatment with the EmboTrap has started is identified as a pretreatment AE (PTAE). An AE that occurs after treatment using EmboTrap has started will be considered a treatment emergent AE (TEAE).

All AEs will be categorized using the Medical Dictionary for Regulatory Activities (MedDRA) Coding of Adverse Events nomenclature. Standardized nomenclature that will be ascertained includes lowest level and preferred MedDRA terms, MedDRA System Organ Class. Adverse Events will be summarised based on their severity and relationship to the treatment (as defined by the treating site), with the relationship categorised as 1) Definite, 2) Probable/Possible and 3) Unlikely. Unrelated adverse events will not be reported. Separate tables will be used to show 1) all adverse events and 2) serious adverse events.

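### SAP 14.1 promises a complete adverse event account but also drops events the unblinded site calls unrelated, so the AE summary can omit non-serious events, including some haemorrhages

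*SAP*

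**What the plan says.** SAP 14.1 opens with a rule that has no relatedness condition: adverse events during or after the procedure, to the 90-day visit, "will be recorded in the database and documented in the Clinical Study Report (CSR"). It then says that events will be adjudicated for relationship, as Protocol 8.3.3 also does: "Note that adverse events will be adjudicated as to the relationship to the EmboTrap device, procedure or the disease state".

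The summary itself is built differently: "Adverse Events will be summarised based on their severity and relationship to the treatment (as defined by the treating site"). Three classes are then allowed, none of them for unrelated events: "with the relationship categorised as 1) Definite, 2) Probable/Possible and 3) Unlikely". The next sentence is "Unrelated adverse events will not be reported", and the table plan comes straight after it: "Separate tables will be used to show 1) all adverse events and 2) serious adverse events".

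Haemorrhage is also read independently of the site. Protocol 6.5.10 gives the core lab the task of detecting and assessing bleeds on CT or MRI: "Hemorrhages will be radiologically classified as described in section 7.1". Protocol 7.1 adds: "Hemorrhages will be classified clinically and radiologically according to the following categories", and lists nine radiological classes from HI 1 to EDH. Under Protocol 12.1 the Clinical Events Committee (CEC) rules on every core-lab haemorrhage as symptomatic or asymptomatic.

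Serious events follow another route. SAP 14.2.1 analyses SAEs and SADEs from CEC data, with a summary of SAEs by preferred term and no filter on relatedness.

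**The concern.** The AE summary is where a reader of the study report looks for harms that fall short of serious. The omission sentence makes entry to that summary depend on a causality call by the team that performed the procedure. There is no blinding and no control arm, so nothing in the design offsets a tendency to attribute events to the stroke rather than to the device or the procedure. Such attribution is easy after thrombectomy, since small haemorrhages can plausibly be put down to the infarct.

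The section also leaves the programmer without a clear instruction. A table titled as containing all adverse events, from which one relationship class has been removed, would mislead a reader who takes the title at face value. At stake is the completeness of the non-serious harm profile, not the trial's primary conclusion.

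**Working it through.** No plan figure is involved and no arithmetic applies. The check is to follow one event through the text.

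**Test event.** A small petechial bleed is seen on the 24-hour scan. There is no NIHSS worsening and it is not serious. The site enters it as an AE and records it as unrelated, attributing it to the stroke.

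**Through SAP 14.1:**

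1. Opening rule: the event is documented in the study report.
2. Relationship categories: there are three, and none fits an unrelated event.
3. Omission sentence: the event is not reported.
4. Table plan: the event belongs in the table of all adverse events.

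Steps 1 and 4 put it in; step 3 takes it out; step 2 gives it no row. Read literally, these cannot all be followed.

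**Through the other planned outputs in the SAP body:**

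- sICH (SAP 5.2.3) needs a worsening of at least 4 NIHSS points or death: not met.
- SADE and PRSAE (SAP 5.2.3) need a serious event: not met.
- SAE and SADE tables (SAP 14.2.1): not met.
- Mortality, new-territory infarction and new-territory embolization (SAP 5.2.3 and Table 1) concern other events.

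For this event, the AE summary is therefore the only specific output in the SAP body where it would appear.

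**Boundary of the effect:**

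- The same bleed called Unlikely stays in, because that category exists.
- A serious event called unrelated by the site still appears in SAP 14.2.1.
- A bleed meeting the sICH definition is counted in its own endpoint and in the primary safety endpoint.

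What is exposed is the set of non-serious events that the site calls unrelated; among haemorrhages, those that are also not sICH.

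**Size.** The number omitted equals the number of non-serious AEs entered by sites multiplied by the share called unrelated. The documents give neither factor. The result runs from zero, if sites call none unrelated, up to every non-serious event so classified.

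**The case against.** The best defence is a softer reading. The omission sentence directly follows the relationship categories, so it may limit only that tabulation. All adverse events is paired with serious adverse events, so it may mean all levels of seriousness rather than all causes. Unrelated events would then be documented somewhere in the report, for example in listings, and left out of the tables. This reading is possible, but the SAP does not state it, and the tables would still be filtered by the site's causality call.

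Other points on that side do stand, and they rule out stronger readings:

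- **Site against CEC.** A reader might infer that the site's view overrides an independent relatedness ruling. For non-serious bleeds it does not. Protocol 12.1 limits the CEC's attribution task to SAEs and to dissections and perforations; for other haemorrhages it lists only symptomatic status. Site relationship for the general summary and CEC data for SAEs and SADEs is largely a division of labour, despite the broad adjudication wording in SAP 14.1 and Protocol 8.3.3.
- **No haemorrhage table planned.** A reader might infer this from the SAP body. It cannot be confirmed, because only the heading of Appendix 2, the listing of tables, is available.
- **Protocol 12.3.1.** It requires AEs to be recorded and reported whatever their cause, but it sits under event notification and governs what sites send to the sponsor. It does not prescribe report tables.
- **Protocol section 12.** It names asymptomatic intracranial haemorrhage, perforation and dissection among procedure-related events to be reported even without clinical sequelae. That makes an unrelated call less likely, especially for vessel injury, but it does not classify every asymptomatic bleed as procedure-related or place it in a SAP table.

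**Conclusion.** The point holds as a defect in the AE reporting rule. SAP 14.1 contains an explicit instruction to leave out events judged unrelated, ties that judgement to the unblinded site, and sits it beside two statements that imply completeness. The consequence is confined to one descriptive summary: non-serious events called unrelated, which can include haemorrhages outside the sICH definition. Primary efficacy, sICH, SADE, PRSAE and the CEC-based SAE results are untouched.

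No figure can be put on the loss. A reader might infer that asymptomatic haemorrhage will be materially under-reported, but any percentage would need an assumed bleed rate and an assumed rate of unrelated calls, and neither has support in the documents.

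Nor would removing the sentence guarantee complete bleed counts. Protocol 12.3.1 has site personnel complete the AE forms, so a bleed seen only by the core lab may never enter the AE data. The conclusion rests on the omission sentence being applied as written; if the programmer follows the table plan instead, nothing entered by the site is lost.

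**What to change.** In SAP 14.1:

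1. Delete the sentence on unrelated events.
2. Add Unrelated as a fourth relationship category, so that the table of all adverse events is complete.
3. Label that table as using site-assessed relationship, and state that the SAE and SADE tables in 14.2.1 use CEC data.

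Optional, if Appendix 2 does not already list it: one descriptive table for treated patients, drawn from core-lab and CEC data, showing any intracranial haemorrhage and asymptomatic haemorrhage by the radiological classes of Protocol 7.1. This is a suggestion rather than a correction, since neither asymptomatic haemorrhage nor bleed grade is a protocol endpoint. Its value is that it does not depend on what sites enter as AEs. If Appendix 2 does list such a table, a cross-reference in SAP 13.2 is enough.

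The required change costs one deleted sentence, one added category and a table label, with no new data. The tables become slightly longer and the harm profile may look less favourable. In the optional table some radiological classes will have few or no events.

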14.2 Deaths, withdrawal, and Serious Adverse Events

14.2.1 Serious Adverse Events and Adverse Device Effects

The analysis of Serious Adverse Events (SAEs) and Serious Adverse Device Effects (SADEs) based on the assessment data provided by the Clinical Events Committee will include:

- An overview of the number of SAEs and number of SADEs recorded in the study. Specifically, the number of patients experiencing at least one SAE and/or at least one SADE, along with whether the patient was withdrawn as a result of either the SAE or the SADE. The information will be summarized using counts and percentages
- Summaries of the number of patients experiencing serious adverse events, by preferred term (counts and percentages)

14.2.2 Withdrawal due to Adverse Events

Withdrawals will be summarised as the number and percentage of patients who were withdrawn from the study due to an adverse event or adverse device effect.

14.2.3 Deaths

Deaths will be summarised as the number and percentage of patients who died within the study period.

14.3 Pregnancies

Pregnancy data will be shown in a data listing. No special analysis will be performed on the pregnancy data. Patients are to be discontinued from the study if they become pregnant.

14.4 Post-Procedure Evaluations

NIHSS and mRS data are collected on the Pre-Procedure form, and again on the 90 Days Follow-Up form. Shift tables will be used to show how these scores changed between the baseline and 90 day follow-up visits.

15 Reporting conventions

P-values ≥ 0.001 will be reported to 3 decimal places; p-values less than 0.001 will be reported as " <0.001 ". The mean, standard deviation, and any other statistics other than quantiles, will be reported to one decimal place greater than the original data. Quantiles, such as median, or minimum and maximum will use the same number of decimal places as the original data. Estimated parameters, not on the same scale as raw observations (e.g. regression coefficients) will be reported to 3 significant figures.

16 References

1. Saver, Jeffrey L., et al. "Solitaire flow restoration device versus the Merci Retriever in patients with acute ischaemic stroke (SWIFT): a randomised, parallel-group, non-inferiority trial." *The Lancet* 380.9849 (2012): 1241-1249.
2. Nogueira, Raul G., et al. "Trevo versus Merci retrievers for thrombectomy revascularisation of large vessel occlusions in acute ischaemic stroke (TREVO 2): a randomised trial." *The Lancet* 380.9849 (2012): 1231-1240.

17 Appendices

Appendix 1: CIP002 rev 05

Appendix 2: Listing of Tables and Data Listings
